6.12 SUBJECT DISPOSITION

Subject disposition will be summarized in terms of the number of participants who were screened, failed screening (by criteria), consented, randomized, treated, completed all follow-up assessments, or discontinued early from the study. Frequency counts and percentages of participants by disposition status will be presented for each cohort and dose level with all data from Placebo participants pooled and summarized as a single group. Disposition will be summarized for the Safety population.

6.12.1 Discontinuations/Early Terminations

All participants who discontinue from the study will be identified, and the extent of their participation in the study will be reported. If known, a reason for their discontinuation will be summarized. Participants who withdraw or are excluded from participation in the study prior to receiving study drug will be replaced; however, withdrawing or terminating participants who have received study drug or placebo will not be replaced.

6.13 DEMOGRAPHIC AND BASELINE CHARACTERISTICS

Demographic characteristics, including age, gender, weight, BMI, race, and ethnicity will be summarized. The subject's age is calculated as the number of years from the subject's date of birth to the date the Informed Consent signed, rounded down to the nearest integer:

$$\text{Age} = \text{Integer} ([\text{Date Informed Consent Signed} - \text{Date of Birth}] / 365.25)$$

Demographics will be summarized for the Safety and PK populations, should these populations be different. Demographic and baseline data will be listed for all participants to supplement summary results. Results will be presented for each cohort and dose level with all data from Placebo participants pooled and summarized as a single group.

6.14 SAFETY ANALYSES

6.14.1 Physical Examination

For the complete physical examination performed at Screening, the proportion of participants reporting results of "Normal", "Abnormal, Not Clinically Significant", and "Abnormal,

Clinically Significant" will be calculated and presented for each body system and cohort/dose level. Any changes between the Screening and SD -1 physical examinations will be captured as part of medical history and any changes between the serial post-dose examinations and the SD -1 physical examination will be captured as an AE and will be presented in those tabulations and/or listings. The proportion of participants that report changes in physical examination between SD -1 and SD 8 will be calculated and presented for each body system and cohort and dose level with all data from Placebo participants pooled and summarized as a single group. The physical examination data will be summarized for the Safety population. A listing of all physical examination results will be provided to supplement the tabulated results.

6.14.2 ECG Data

Descriptive statistics of ECG results (ventricular HR, PR interval, QRS interval, QT interval, QTcF interval) will be calculated at each scheduled time point and will include the change from baseline. The summary of descriptive statistics at each time point will be displayed by cohort and dose level, with all data from Placebo participants pooled and summarized as a single group.

In addition, the frequency and percentage of participants classified as "Normal", "Abnormal, Not Clinically Significant" or "Abnormal, Clinically Significant" will be summarized at each time point. The frequency and percentage of participants with ECGs that are classified as "Normal" at baseline but change to "Abnormal, Clinically Significant" or "Abnormal, Not Clinically Significant" after dosing, or that are classified as "Abnormal, Not Clinically Significant" at Baseline but change to "Abnormal, Clinically Significant" after dosing will also be summarized.

ECG results and changes from baseline in ECG results will be categorized with the number and proportion of participants reporting changes presented as categorical variables.

The ECG data will be summarized for the Safety population and a listing of all ECG data will be provided to supplement the tabulated results.

6.14.3 Vital Signs

Descriptive statistics of vital signs (pulse rate, BP, temperature, respiratory rate, pulse oximetry) will be calculated at each scheduled time point and will include the change from baseline. The summary of descriptive statistics at each time point will be displayed by cohort and dose level, with all data from Placebo participants pooled and summarized as a single group. The vital signs data will be summarized for the Safety population and a listing of all vital signs data will be provided to supplement the tabulated results.

6.14.4 Clinical Laboratory Tests

Descriptive statistics of clinical laboratory tests (serum chemistry, hematology, and urinalysis) will be calculated at each scheduled time point and will include the change from baseline for each analyte. The summary of descriptive statistics at each time point will be displayed by cohort and dose level, with all data from Placebo participants pooled and summarized as a single group for each analyte.

In addition, shift tables summarizing changes from normal to out-of-normal range will be provided. -

The laboratory data will be summarized for the Safety population and a listing of all laboratory data will be provided to supplement the tabulated results.

6.14.5 Adverse Events

Treatment-emergent AEs (TEAEs) are defined as those AEs with onset date and time equal to or after start of study medication or those events in which the onset date and time are before the start of study medication but worsened after the start of study medication. To be conservative, in the case of a missing onset time for an AE, an AE with a start date equal to or after the dosing date will be considered treatment-emergent. All AEs will be coded using the MedDRA dictionary, version as noted in the Data Management Plan, using System Organ Class and Preferred Terms.

All TEAEs will be summarized by cohort and dose level, with all data from Placebo participants pooled and summarized as a single group. The number of TEAEs as well as the number and percentage of participants who experienced at least one TEAE will be summarized for each system organ class and each preferred term. The percentage will be based on the number of safety participants in a particular treatment group. Each subject will contribute at most one count per summarization category. All TEAEs will be sorted in descending order of the incidence rate of system organ classes in the highest dosing group and then within each system organ class by descending order of incidence rate of preferred terms in the same group. TEAEs potentially related to study medication, serious TEAEs, and TEAEs leading to withdrawal will be summarized in a similar manner. A separate table will present all TEAEs that are coded as unexpected and possibly, probably, or definitely related to treatment.

If a subject has more than one AE that codes to the same preferred term, the subject will be counted only once for that preferred term. Similarly, if a subject has more than one AE within a system organ class category, the subject will be counted only once in that system organ class category.

TEAEs will also be summarized by maximum severity and by strongest relationship to treatment within each cohort and dose level. SAEs will be tabulated and listed in a manner similar to TEAEs. The AE data will be summarized for the Safety population and a listing of all AE data will be provided to supplement the tabulated results.

6.14.6 Neuropsychiatric Scales

Descriptive statistics (mean, standard deviation, minimum, maximum, median) of scores on the neuropsychiatric status assessments (BPRS and C-SSRS) will be presented for each timepoint by dosing group (placebo, 0.005, 0.007, 0.011, 0.014, 0.021mg/kg).

As the RASS will only be used if general agitation or sedation are reported, the number of participants with RASS performed, the reason for performance of the RASS, the time since injection when the RASS was administered, the RASS score, the resulting action taken (e.g., rescue drug administered, resolved or unresolved) will be presented by dose group and overall.

Signal neuropsychiatric events defined as DLTs (BPRS ≥ 40 or item score ≥ 4 at 48-hour post-dose evaluation) or symptoms (e.g., delirium, paranoia, and/or hallucinations) defined as adverse events will be noted and the affected participants' BPRS, C-SSRS, and RASS (if applicable) scores will be presented at each time point in relation to the determination of the event.

Change in BPRS scores from baseline (when BPRS≤25) will be compared for each dose level to placebo. Each time-point will be modeled separately. Changes in BPRS scores will be compared between each dose and the placebo group using a Wald test of coefficients from ANOVA.

Change in C-SSRS scores at SD 8 (from a baseline of zero) will be assessed. The proportion of individuals having a change in score from zero will be compared for each drug dosage level to the placebo group using Fisher's exact test. Scores for all participants receiving active Scop HBT will be compared to those receiving placebo.

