ⁿ Continuous cardiovascular monitoring of ECG (3-lead) and vital signs (blood pressure (at 5-15 min intervals), heart rate, respiration rate, and pulse oximetry) from 1 hour prior to dosing through 24 hours post dose (see [Table 4](#) and Section [11.1.2](#) for details).

^o Injection site assessments: Subject will be asked to rate the maximum intensity of pain, pruritus, tingling, and numbness using the VAS. See [Table 4](#) for assessment time points from pre dose through 24 hours post dose. Immediately following the subjective assessment, an assessment of pain, tenderness, erythema, and induration at the injection site will be performed by a physician, physician assistant, or nurse.

^p See [Table 4](#) for assessment time points on Day 1. For items assessed over time (eg, items 1, 2, and 3), the period of assessment should be “over the prior week,” except for the assessments performed at 6-8 and 48 hours post dose, which should be assessed “since the prior assessment.”

^q C-SSRS will be assessed at screening, Day -1 (baseline), and Day 8.

^r RASS will be used to assess alertness/level of consciousness at 1 hour post dosing (+30 min) (see footnote ^e above), and at other times for severity if AEs of general agitation or sedation occur.

^s SCID-5-CT will be administered at Day -1 to identify the presence of any major DSM-5 Axis I or II disorder. Note: Alternates who return for dosing on another day will not have the SCID repeated.

^t The DSST will be administered at screening, baseline, 48 hours post dose, and Day 8 to detect any persistent cognitive impairment. The DSST will not be used to determine eligibility.

Table 4: Study Events Schedule – Pre Dose through 36 Hours Post Dose

Activity/Assessment	Pre Dose	Dosing = Time 0	Minutes Post-dose							Hours Post-dose									
			2	5	10	15	20	30	45	1	1.5	2	3	4	5	8	12	24	36
ECG	X			X	X	X		X	X	X	X		X		X	X	X	X	
Vital Signs	X			X	X	X		X	X	X	X		X		X	X	X	X	
Abbreviated Physical or Brief Neurological Exam ^a	X									X									
Injection Site: VAS ^b	X			X	X	X		X	X	X	X		X		X	X	X	X	
Injection Site: Physician, Physician Assistant or Nurse	X			X	X	X		X	X	X	X		X		X	X	X	X	
BPRS ^c																			6
C-SSRS																			
RASS ^d			At 1 hour post-dosing (+30 min) and as needed to assess severity only if adverse events of general agitation or sedation occur																
Final Eligibility	X																		
Eligibility Checklist	X																		
Randomization	X																		

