Urine PK Samples ^e	X		0-4 h										4-12 h			12-24 h			
Blood PK Samples	X		X	X	X	X	X		X		X		X		X	X	X	X	
Safety Lab Tests																			X
Adverse Events	X		X	X	X		X	X	X	X		X		X	X	X	X		
Concomitant Medications	X		X	X	X		X	X	X	X		X		X	X	X	X		
Continuous Cardiovascular Monitoring	Begin		ECG (3-lead) and vital signs (blood pressure (5-15 min intervals), heart rate, respiration rate, and pulse oximetry)(see Section 11.1.2 for details)														End		

Error! Reference source not found. Abbreviated physical exam at pre-dose; brief neurological assessment at 1 hour post dosing (+30 min) to assess alertness, orientation, ability to follow commands and coordination (refer to Section 11.1.5 and footnote ^d below).

^b If the PI or designee determines a subject is incapable of providing valid responses on the VAS due to the neuropsychiatric effects of Scopolamine HBT, the reason(s) why the VAS assessment(s) could not be done will be documented by time point in the source.

^c BPRS will be performed at 6 (+ 2) hours post dose. The + 2-hour window is provided to allow the investigator some discretion should the assessment need to be delayed or cannot be performed. The timing may be dependent on the emergence and severity of neuropsychiatric symptoms. The reason(s) why the BPRS was delayed or could not be done will be documented in the source.

^d RASS will be employed as part of the brief neurological assessment at 1 hour post dosing (+30 min) to assess alertness/level of consciousness, and at other times if adverse events of agitation or sedation occur.

^e Record the time and estimated volume of individual voids from pre dose through 24 hours post dose. This information will assist in the assessment of urine output and hydration, and will subsequently be used to calculate the total volume of urine pooled for each PK collection interval. Refer to Section 9.1.1.3 for details.

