11.1.5. Physical Examination

Each subject will have a complete physical examination at screening, Day -1, and Day 8. Abbreviated (targeted) physical examinations will be performed as needed prior to dosing on Day 1 and prior to discharge on Day 3. A complete physical examination includes all major systems, including general appearance, EENT, chest/respiratory, heart/cardiovascular, abdomen/gastrointestinal, lymph nodes/spleen, genitourinary, musculoskeletal, skin, neurological, and hepatic. The screening physical exam includes an assessment of upper leg

muscle tissue (ie, adequacy of tissue for IM injection). Targeted physical examinations may be performed at other times as deemed necessary by the investigator.

In addition, at the request of the DSMB for Cohorts 3-5, a brief neurological assessment will be performed at 1 hour post dosing (+30 min) on Day 1 to assess alertness/level of consciousness, orientation, ability to follow commands and coordination. The assessment will be documented in the subject's medical record. At the end of each cohort, the PI will provide narratives (per cohort and subject) for inclusion in the DSMB data reviews.

The brief neurological assessment will be performed as follows in this sequence:

- 1) To assess alertness and level of consciousness, the RASS ([Appendix D](#)) will be employed and the completed scale will be added to the subject's medical record.
The RASS score will be entered into the eCRF; however, the scores for orientation and ability to follow commands (see below) will not be entered into the eCRF.
- 2) Orientation will be assessed using questions 1 and 2 of the Folstein Mini-Mental Status Examination ([Rovner and Folstein, 1987](#)), as shown below. The answers to each question will be noted in the subject's medical record, along with the combined score for the two questions. Scoring will be performed according to Rovner and Folstein ([1987](#)).
 - “What is the year? Season? Date? Day of the week? Month?”
 - “Where are we now: State? County? Town/city? Hospital? Floor?”
- 3) Ability to follow commands and coordination (to the extent possible) will be assessed using a modified question 8 of the Folstein Mini-Mental Status Examination as shown below. The total score will be noted in the subject's medical record. Scoring will be performed according to Rovner and Folstein ([1987](#)).
 - “Take the paper in your right hand, fold it in half, and hand it back to me.”

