^o Injection site assessments: Subject will be asked to rate the maximum intensity of pain, pruritus, tingling, and numbness using the VAS. See [Table 2](#) for assessment time points from pre dose through 24 hours post-dose. Immediately following the subjective assessment, an assessment of pain, tenderness, erythema, and induration at the injection site will be performed by a physician, physician assistant, or nurse.

^p See [Table 2](#) for assessment time points on Day 1. For items assessed over time (e.g., items 1, 2, and 3), the period of assessment should be “over the prior week,” except for the assessments performed at 6-8 and 48 hours post dose, which should be assessed “since the prior assessment.”

^q C-SSRS will be assessed at screening, Day -1 (baseline), and Day 8.

^r RASS will be used to assess severity only if AEs of general agitation or sedation occur.

^s SCID-5-CT will be administered at Day -1 to identify the presence of any major DSM-5 Axis I or II disorder.

^t The DSST will be administered at screening, baseline, 48 hours post dose, and Day 8 to detect any persistent cognitive impairment. The DSST will not be used to determine eligibility.

Table 2: Study Events Schedule – Pre-Dose through 36 Hours Post Dose

Activity/Assessment	Pre-Dose	Dosing = Time 0	Minutes Post-dose							Hours Post-dose									
			2	5	10	15	20	30	45	1	1.5	2	3	4	5	8	12	24	36
ECG	X			X	X	X		X	X	X	X		X		X	X	X	X	
Vital Signs	X			X	X	X		X	X	X	X		X		X	X	X	X	
Abbrev Physical Exam	X																		
Injection Site: VAS ^a	X			X	X	X		X	X	X	X		X		X	X	X	X	
Injection Site: Physician, Physician Assistant or Nurse	X			X	X	X		X	X	X	X		X		X	X	X	X	
BPRS ^b																	6		
C-SSRS																			
RASS																			
Final Eligibility	X																		
Eligibility Checklist	X																		
Randomization	X																		
Urine PK Samples	X																		
Blood PK Samples	X																		
Safety Lab Tests																			
Adverse Events	X																		
Concomitant Medications	X																		
Continuous Cardiovascular Monitoring	Begin																		
ECG (3-5 lead) & vital signs (blood pressure, heart rate, respiration rate, & pulse oximetry)																End			

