5.1.8 Neuropsychiatric/Behavioral Assessments

Assessments of neuropsychiatric/behavioral symptoms will be performed by study staff using the C-SSRS, BPRS (expanded version 4.0, 24 items), and RASS (if general agitation or sedation are reported). A psychiatrist will be available on-site to consult with the investigator throughout the study. At the investigator's request, the psychiatrist will come to the clinic to evaluate a subject.

The C-SSRS Baseline/Screening version will be administered by a physician, physician assistant, or nurse at screening, and the C-SSRS Since Last Visit version will be administered at SD -1 and at follow-up on SD 8. Scoring and analysis will be performed according to the Columbia-Suicide Severity Rating Scale Scoring and Data Analysis Guide. Study staff administering the C-SSRS will complete C-SSRS training. The C-SSRS has excellent inter-rater reliability².

The BPRS will be performed by a psychologist or trained clinician. The BPRS will be assessed at screening, SD -1 (baseline), at 6 (+ 2) hours post dose (timing at the discretion of the investigator or designee), 48 hours post dose (prior to discharge), and on SD 8. In order to improve reliability between administrations, a structured interview guide will be used and the same clinician will administer the BPRS to each participant. For BPRS items assessed over time (e.g., items #1, 2, and 3), the reference period of assessment should be over the prior week, except for assessments performed at 6 and 48 hours post dose, which will be assessed since the prior assessment. The BPRS has low inter-rated reliability, and measures will be taken to ensure that it is captured consistently over time.

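### The SAP treats every RASS as triggered by an adverse event, but the protocol schedules one at 1 hour in Cohorts 3-5, so the planned table mixes two kinds of score across a dose boundary

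*SAP*

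**What the plan says.** The SAP describes RASS as triggered in three places. Footnote r to the schedule in SAP 3.2 reads "RASS will be used to assess severity only if AEs of general agitation or sedation occur". SAP 5.1.8 lists the scale as "RASS (if general agitation or sedation are reported"). SAP 6.14.6 opens its RASS paragraph with "As the RASS will only be used if general agitation or sedation are reported" and then plans to present, by dose group and overall, the number of participants assessed, the reason, the time since injection, the score and the action taken.

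The protocol schedules it. Section 11.1.5 states that "at the request of the DSMB for Cohorts 3-5, a brief neurological assessment will be performed at 1 hour post dosing (+30 min"). The first step of that assessment is a RASS, no adverse event is needed to start it, and "The RASS score will be entered into the eCRF". Footnote r to Protocol Table 3 agrees: "RASS will be used to assess alertness/level of consciousness at 1 hour post dosing (+30 min"), and at other times for severity if agitation or sedation occurs. Footnote d to Table 4 repeats it: "RASS will be employed as part of the brief neurological assessment at 1 hour post dosing (+30 min").

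Protocol 12.1.2 plans descriptive statistics for RASS, if conducted, at each dose level and time point. SAP 6.14.6 gives such statistics only for BPRS and C-SSRS. SAP section 1 says that the SAP prevails where the two differ and that differences are described in SAP 6.2, which mentions none for RASS.

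**The concern.** A count of participants with a RASS can be read as a safety signal only if the reason for doing one is the same in every column. Here it changes from only those with agitation or sedation to everyone, and under Protocol 11.1.5 it changes between 0.007 and 0.011 mg/kg. A reader going across the dose columns would see a step that comes from the schedule. The scores are affected the other way: at the two lower doses they come only from subjects with symptoms, and at the three higher doses they also include subjects who were alert and calm.

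What is at stake is a clear description of early alertness and agitation. Safety and tolerability is a primary objective, and the DSMB asked for this assessment. As the SAP stands, no described output gives the scheduled 1-hour score a fixed denominator and a matching placebo group.

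**Working it through.** The documents state no figure for this point, so there is none to reproduce. The check compares the texts and counts subjects.

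**Inputs**
- Per cohort: 6-9 active and 2-3 placebo, 8-12 in all (SAP 3.4).
- Cohorts 1-2 are 0.005 and 0.007 mg/kg; Cohorts 3-5 are 0.011, 0.014 and 0.021 mg/kg (Protocol Table 7).
- One placebo column: SAP 6.14.6 lists its dosing groups for BPRS and C-SSRS as placebo plus five doses. I take the RASS table to follow the same layout.

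**Who has a scheduled RASS under Protocol 11.1.5**
- Active: 3 × (6 to 9) = 18-27.
- Placebo: 3 × (2 to 3) = 6-9.
- Total: 3 × (8 to 12) = 24-36.

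**Who can have only a triggered RASS**
- Active: 2 × (6 to 9) = 12-18.
- Placebo: 2 × (2 to 3) = 4-6.

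The placebo column of 10-15 subjects therefore combines 6-9 assessed by schedule with 4-6 assessed only after an event.

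**Illustration with no dose effect.** Assume the same true probability q of agitation or sedation in every group, including placebo. Give each subject with an event an absolute RASS of 1, present at the assessment, and everyone else 0. The documents give no value for q, so a range is shown. Use unexpanded cohorts (6 active each; 10 placebo, of whom 6 are scheduled).
- Expected number assessed per active group: 6q in each of Cohorts 1-2, and 6 in each of Cohorts 3-5.
- Mean absolute score among those assessed: 1 in Cohorts 1-2, and q in Cohorts 3-5.
- Pooled placebo: expected number assessed 6 + 4q; mean approximated by 10q / (6 + 4q).

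| q | Assessed of 6, Cohorts 1-2 | Assessed of 6, Cohorts 3-5 | Mean score, Cohorts 1-2 | Mean score, Cohorts 3-5 | Placebo assessed of 10 | Placebo mean score |
|---|---|---|---|---|---|---|
| 0.10 | 0.6 | 6 | 1.00 | 0.10 | 6.4 | 0.16 |
| 0.25 | 1.5 | 6 | 1.00 | 0.25 | 7.0 | 0.36 |
| 0.50 | 3.0 | 6 | 1.00 | 0.50 | 8.0 | 0.625 |
| 0.75 | 4.5 | 6 | 1.00 | 0.75 | 9.0 | 0.83 |

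With no dose effect at all, the number assessed rises at the boundary and the score looks milder above it. The placebo mean matches neither set of active columns, although the true rate is the same everywhere.

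**Which protocol text governs.** Only 11.1.5 names Cohorts 3-5. Tables 3 and 4 and section 9.1.1.3 give the 1-hour assessment without a cohort limit, and section 7.1 lists RASS only on an adverse event. If the unrestricted text applied, all 5 × (8 to 12) = 40-60 subjects would have a scheduled RASS. The dose imbalance would then vanish, but the SAP premise would still be false.

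**The case against.** The strongest reply is that the planned table already carries what is needed to tell the two kinds apart. A scheduled RASS would show its own reason and a time near 1 hour, and a careful reader could sort them. That stands in part. However, the SAP neither stratifies by reason nor sets denominators, and its text allows for no reason other than an event. The shells are in a separate document, so whether they already split RASS by time point cannot be checked.

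It is also fair that this is a descriptive table. RASS is in none of the 110 tests in SAP Table 7, and the DSMB uses no statistical test. A reader might infer that inference or escalation is compromised; the documents do not support that.

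Two further inferences are tempting. One is that the 1-hour RASS is the only rating near peak effect. No document gives the time of peak CNS effect after IM dosing. Protocol 5.2.4 cites an IV study in which alertness lagged plasma with an equilibration half-life of 2.5 to 3.5 hours. Adverse events are also asked about at 11 time points from 5 minutes to 12 hours (Protocol 9.1.1.3).

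The other is that the remaining 1-hour scores are wrongly lost. The protocol says openly that "the scores for orientation and ability to follow commands (see below) will not be entered into the eCRF". They are not listed endpoints, no pre-dose score is scheduled, and investigator narratives go to the DSMB reviews. Leaving them in the medical record is a design choice, and reversing it would need a protocol modification.

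**Conclusion.** The point holds as a mismatch between protocol and SAP with a real effect on one descriptive output. The SAP premise is wrong on any reading that includes the scheduled assessment. On the specific text of 11.1.5, 24-36 subjects have a RASS that the SAP does not provide for. Apart from missed assessments, 100% would be assessed at 0.011 mg/kg and above, against adverse-event cases only at 0.005 and 0.007 mg/kg, with placebo mixed.

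The dose imbalance rests on the Cohorts 3-5 limit, which appears in one place. The tabulated values also rest on an assumed event rate and a simplified score; they show the direction of the distortion and do not forecast its size. No p-value or multiplicity threshold changes.

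The likely cause is that the SAP text was not updated when the DSMB's request was added: SAP section 1 ties the SAP to protocol version 2.0, and its schedule has no 1-hour neurological assessment. That is an inference.

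**What to change.** - **SAP 3.2 and 5.1.8:** add the scheduled 1-hour RASS beside its use after agitation or sedation events.
- **SAP 6.14.6:** summarise the scheduled RASS by dose and time point for Cohorts 3-5, with placebo from Cohorts 3-5 only as the comparison and the number scheduled as the denominator. Keep the existing table, for all cohorts, for event-triggered RASS only. The rescue-medication rule in SAP 6.11 can apply unchanged.
- **Protocol:** reconcile section 7.1 (event only) and Tables 3-4 and 9.1.1.3 (no cohort limit) with 11.1.5 (Cohorts 3-5). If all cohorts are meant, the scheduled table covers all five doses and all placebo subjects.

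The cost is wording in three SAP sections, one extra descriptive table and a protocol clarification. The RASS scores are already in the eCRF, so no new data are needed. The change should be made before unblinding, because SAP 6.2 would otherwise class it as post hoc.

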12.1.2. Safety Analyses

Safety analysis will include data collected from the safety analysis set. DLT and AE data will be coded using the current MedDRA version at the time of study setup, listed individually (including intervention and outcome), and summarized by system organ class and preferred terms within a body system for each treatment group. Data will be summarized by both event (counting each event regardless of subject) and by subject (counting only one event within each system organ class or preferred term). Serious and/or unexpected AEs will also be discussed on a case-by-case basis.

Changes in pulse rate, systolic and diastolic blood pressure, weight, and respiratory rate will be summarized (mean, median, minimum, maximum, standard deviation) by dose level and time point. Clinical laboratory assessment results will be presented.

Upper bounds of 80% confidence intervals of the true probability of events (extreme DLTs, non-extreme DLTs, and severe AEs) will be estimated from the number of events in each cohort using the Pearson-Clopper method.

Descriptive statistics of BPRS, C-SSRS, DSST, RASS (if conducted), and injection site VAS scores (mean, median, standard deviation, minimum, and maximum) will be presented for each dose level and time point.

Changes in the BPRS score (6 hours, 48 hours, and 8 days) from baseline will be compared between placebo and active dose levels using ANOVA models for each time point. The null hypothesis of no difference between placebo and the active dose will be tested for each dose level using a one-sided alternative hypothesis of higher increases among the participants receiving the active drug than among the placebo group.

Participants have C-SSRS scores of zero at baseline. The proportion of individuals having any increase in their C-SSRS score from zero will be compared for each drug dosage level to the placebo group using Fisher's exact test.

The DSST will be conducted at screening, Day -1, Day 3, and Day 8. Changes from baseline (Day -1) will be compared between placebo and active dose levels using ANOVA models for each time point. Placebo control will help to exclude any remaining practice effects or changes

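### The SAP's count of subjects with a RASS assumes event-triggered use only, but the protocol schedules a 1-hour RASS for Cohorts 3-5, so the count by dose group largely reflects the schedule

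*SAP*

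**What the plan says.** SAP 6.14.6 opens its RASS paragraph with "As the RASS will only be used if general agitation or sedation are reported, the number of participants with RASS performed". It then adds further items, among them "the reason for performance of the RASS, the time since injection when the RASS was administered", together with the score and the action taken. All of these "will be presented by dose group and overall". SAP Table 1 footnote r carries the same premise: "RASS will be used to assess severity only if AEs of general agitation or sedation occur". SAP 5.1.8 repeats it in brackets after naming the scale.

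The protocol is different. Section 11.1.5 states that "at the request of the DSMB for Cohorts 3-5, a brief neurological assessment will be performed at 1 hour post dosing", with a 30-minute late allowance on Day 1. The first step of that assessment is a RASS. It does not depend on an adverse event, and its score is entered in the eCRF, whereas the orientation and command scores are not.

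The protocol's schedule text also has the routine RASS but names no cohorts. Table 3 footnote r says "RASS will be used to assess alertness/level of consciousness at 1 hour post dosing (+30 min" and adds event-triggered use at other times. Table 4 footnote d and section 9.1.1.3 agree with it. Protocol 7.1 still lists the RASS only for reported agitation or sedation.

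**The concern.** The SAP's reason for tabulating how many subjects had a RASS is that having one implies a report of agitation or sedation. Under protocol 11.1.5 this fails for three of the five dose groups, and for the placebo subjects enrolled with them. A reader of the planned table who trusts its stated premise would see few assessments at the two lowest doses and complete assessment at the three highest, and could take the difference as a drug effect.

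The scheduled score itself also has no proper place in the SAP. Section 6.14.6 gives statistics by time point for the BPRS and C-SSRS, not for the RASS. Yet the 1-hour RASS is the earliest scheduled neuropsychiatric score after dosing: the BPRS is next at 6 (+2) hours and the DSST at 48 hours. Protocol 11.1.6 says that general agitation and sedation match no specific BPRS item. Characterising safety across doses is a primary objective, so this score deserves a summary against the right placebo subjects.

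**Working it through.** The plan states no figure for the number of subjects with a RASS, so there is none to reproduce. The cohort totals used below do check: 5 × 6 = 30 to 5 × 9 = 45 active, and 5 × 2 = 10 to 5 × 3 = 15 placebo, as in SAP 3.4.

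**Inputs.** 6 active and 2 placebo per 8-subject cohort, or 9 and 3 if expanded (SAP 3.4, 3.6). Placebo is shown as one group (SAP 6.14.6). Scheduled RASS in Cohorts 3-5 only (protocol 11.1.5). The proportion of subjects with an event-triggered RASS, q, is not given in the documents. It is assumed equal in all groups, meaning no drug effect, and varied from 0% to 50%.

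**Formulas.** Expected proportion with a RASS:
- Cohorts 1-2, active: q
- Cohorts 3-5, active: 1 (everyone is already counted)
- Pooled placebo: (3/5) × 1 + (2/5) × q = 0.6 + 0.4q

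**No events at all (q = 0).**

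| Group | 8-subject cohorts | 12-subject cohorts |
|---|---|---|
| 0.005 mg/kg | 0/6 | 0/9 |
| 0.007 mg/kg | 0/6 | 0/9 |
| 0.011 mg/kg | 6/6 | 9/9 |
| 0.014 mg/kg | 6/6 | 9/9 |
| 0.021 mg/kg | 6/6 | 9/9 |
| Pooled placebo | 6/10 | 9/15 |
| Overall | 24/40 | 36/60 |

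Placebo: 3 cohorts × 2 = 6 of 5 × 2 = 10. Overall: 3 × 8 = 24 of 5 × 8 = 40.

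**Equal background rate q in every group.**

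| q | Cohorts 1-2 active | Cohorts 3-5 active | Pooled placebo | Step (1 − q) |
|---|---|---|---|---|
| 10% | 10% | 100% | 64% | 90 points |
| 30% | 30% | 100% | 72% | 70 points |
| 50% | 50% | 100% | 80% | 50 points |

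Across this range pooled placebo lies above the two lowest doses and below the three highest, although the drug does nothing in this calculation.

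**Other reading of the protocol.** If the schedule tables apply without a cohort limit, every group shows 100%. The step vanishes, but the count carries no information and still contradicts the SAP's premise.

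**After separation.** Counting only event-triggered RASS gives an expected proportion q in every group, placebo included. If Cohorts 3-5 are the ones covered, the scheduled score has 3 × 6 = 18 to 3 × 9 = 27 active subjects and 3 × 2 = 6 to 3 × 3 = 9 placebo subjects from the same cohorts.

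**The case against.** The best defence is that the count does not stand alone. SAP 6.14.6 also presents the reason, the time since injection and the score. In the no-event case the same output would show scores of 0 at about 1 hour, and a careful reader could work out that these were routine. This stands in part. However, the SAP defines no reason category for a scheduled assessment, and protocol 11.1.5 names only the score as entered in the eCRF. The table shells are in a separate document, so it cannot be confirmed that the reason is captured in usable form. The count row remains mixed either way.

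A second objection is that 0/6 against 6/6 is the extreme case. That is right. Protocol 5.3.1.2 expects drowsiness at 0.005-0.007 mg/kg, so triggered assessments in Cohorts 1-2 are plausible and would shrink the step.

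Third, nothing inferential depends on this. SAP Table 7 contains no RASS test, the DSMB uses no statistical tests, and it receives narratives of the neurological assessments. This stands in full.

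A reader might also infer that an average RASS would hide agitation and sedation cancelling out, because protocol 12.1.2 lists "Descriptive statistics of BPRS, C-SSRS, DSST, RASS (if conducted), and injection site VAS scores" for means. The documents do not support this as a fault in the planned output. SAP section 1 says that the SAP supersedes the protocol where analyses differ, and 6.14.6 plans no mean RASS. Protocol 12.1.2 would in any case also show the standard deviation, minimum and maximum.

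**Conclusion.** The SAP's premise for the RASS table is wrong under the current protocol, and the planned count by dose group would be driven by the assessment schedule. With 8-subject cohorts and no events it shows a jump from 0/6 to 6/6 between 0.007 and 0.011 mg/kg, with pooled placebo at 6/10. This rests on the Cohorts 3-5 limit, which appears only in protocol 11.1.5, and on the trial reaching Cohort 3. Without that limit the count is 100% throughout and uninformative. The correction is needed on either reading.

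The effect is confined to a descriptive table, and the reason, time and score items soften it. Three stronger readings are not supported:
- A graded dose trend: the artefact is one step, with no rise within Cohorts 3-5.
- That the SAP declares the count to be a measure of agitation or sedation: it states the premise and tabulates the count beside other items.
- That the 1-hour score is taken near peak effect: the documents give no time of peak sedation after intramuscular dosing. An intravenous study described in protocol 5.2.4 reports an equilibration half-life of 2.5 to 3.5 hours for alertness. Earliest scheduled score is as far as the text goes.

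**What to change.** 1. Reconcile protocol 11.1.5 with Table 3 footnote r, Table 4 footnote d, 9.1.1.3 and 7.1 on which cohorts have the scheduled RASS.
2. Correct SAP 5.1.8, Table 1 footnote r and 6.14.6 so that they describe both uses of the scale.
3. Report the scheduled 1-hour RASS as a distribution by dose, for example the numbers with negative, zero and positive scores, with minimum and maximum. Compare it with placebo subjects from the same cohorts only. The cut-points are a suggestion; any display that keeps the two directions apart will do.
4. Report event-triggered RASS separately for all cohorts with the items already listed in 6.14.6. Use a reason category of scheduled 1-hour or AE-triggered. If the reason was not captured, derive it from the adverse event records and the assessment time, and state how an event falling in the 1-hour window is classified.

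A note under the second table should say that a scheduled check may itself bring agitation or sedation to light, so surveillance is not identical across cohorts even after the split.

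The cost is SAP wording, a revised table shell and a clarification of the protocol text. The split requires no new assessments, and no hypothesis test or multiplicity threshold changes.
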